6.1.2.4 Average length of stay (in days) of children admitted to hospital

Length of stay is defined as hospitalisation duration in days as reported by the caregiver at Day 7 and Day 28. If a child is hospitalised twice, the first hospitalisation will be used and second hospitalisations will be reported separately. The denominator will be all hospitalised children.

6.1.2.5 Proportion of children referred by a primary healthcare provider to a higher level of care at Day 0 consultation

All children who received a referral advice (as per definition above) at Day0 will be counted in the numerator. The denominator will be all children recruited.

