Quantitative research assistants will conduct the phone follow-up interviews using an EDC mobile application. Personally identifiable information (PII) will be used for contacting caregivers. No time window applies to Day 7 follow-up. A window of +7 days applies to Day 28 phone call attempts (Day 28 to Day 35).

Data that will be collected at Day 7 follow-up will include cure status (recovery from illness as reported by the caregiver), death and hospitalization information between Day 0 and Day 7 as

reported by caregivers. The primary outcomes on the proportion of children with severe complications by Day 7 and on the proportion of children admitted to hospital within 24 hours of the Day 0 primary care consultation as a result of a referral will be assessed based on Day 7 follow-up. Hospital name, duration of hospitalization and reason for admission will be collected for children reported to have been hospitalized to facilitate the retrospective data collection at referral hospital level.

Data collected at Day 28 follow-up will include death and hospitalization information as reported by the caregiver. The secondary outcome on the proportion of children with severe complications at Day 28 will be assessed on the basis of this interview.

Higher level of care visit

Data collection will be conducted retrospectively at all government-designated and private referral facilities within the study area, including hospitals or emergency / inpatient area of larger primary or secondary care facilities (e.g., study facilities that can admit paediatric patients). A quantitative research assistant using the EDC mobile application will collect data from referral facility records, registries and discharge summaries to document hospitalization for all children reported to have been hospitalized between Day 0 and Day 7. Personally identifiable information will be collected to cross-check the identity of the patients. Arrival date and time, basic clinical information on arrival and, if admitted, admission and discharge diagnosis, and admission duration and outcome will be collected. If available, data on oxygen saturation at admission, oxygen administration and intensive care unit (ICU) admission and duration will also be recorded.

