6.2 Analysis Methods

6.2.1 Analytical Methods

Outcomes will be described by arm using summary statistics. In particular, counts and percentages will be used for binary variables and reported with one decimal place; mean and standard deviation (SD) or median (IQR) for continuous variables depending on their distribution. Mean and median will be displayed with one decimal place and SD and IQR will be presented with two decimal places.

The two primary outcomes will be assessed using a random effects logistic regression model with the cluster included as a random effect. If convergence issues arise due to sparse data, clusters may be dropped or combined to higher grouping level (e.g. district).

Results will be reported with odds ratios, risk differences and their associated 95% confidence intervals (CI). The control arm will be used as reference category.

Secondary outcomes and other binary outcomes of interest will be evaluated in the same way.

Other continuous outcomes of interest will be assessed using random effects linear regression model with the cluster included as a random effect. Results will be reported in terms of adjusted mean differences between arms with associated 95% CIs.

Modelling of secondary outcomes will be performed if numbers allow.

For interim analyses and DMC analyses, only the two primary outcomes will be presented. Modelling will not be performed and results will be reported in terms of summary statistics only.

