6.2.2 Adjustment for Covariates

All models will be adjusted for stratification factors (facility type, location) and baseline variables that are found to be randomly imbalanced across arms. As described in Section 5.5, the imbalance will only be assessed visually and without performing any formal comparison.

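### Length of stay is compared between arms only among hospitalised children, a group the intervention is meant to change, so the contrast mixes who is admitted with how long they stay

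*SAP*

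**What the plan says.** SAP 6.1.2.4 takes the duration from the caregiver: "Length of stay is defined as hospitalisation duration in days as reported by the caregiver at Day 7 and Day 28". For a child admitted twice, "the first hospitalisation will be used and second hospitalisations will be reported separately". On who is counted, it says: "The denominator will be all hospitalised children".

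SAP 6.2.1 gives the model: "Other continuous outcomes of interest will be assessed using random effects linear regression model with the cluster included as a random effect". It continues: "Results will be reported in terms of adjusted mean differences between arms with associated 95% CIs". In the outcome list of SAP 3.1.4, length of stay is the only continuous outcome and every other item is a proportion, so this model applies to it. On covariates, SAP 6.2.2 says: "All models will be adjusted for stratification factors (facility type, location) and baseline variables that are found to be randomly imbalanced across arms". Severity at admission is not named.

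SAP 6.1.1 counts a child as hospitalised if that is the child's status at the follow-up call, so some stays will still be running when reported. SAP 6.1.2.4 does not say which report prevails or how such a stay is completed. Protocol 8.1.1 provides a second source, facility records, from which "admission duration and outcome will be collected". The SAP definition does not use it.

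**The concern.** Admission is an effect of the intervention. Co-primary outcome 2 is referred admission within 24 hours, and co-primary outcome 1 includes secondary hospitalisation. If either moves, the hospitalised children in the two arms are different mixtures. Adjusting for stratification factors and baseline imbalances does not restore comparability, because the selection happens after randomisation.

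The protocol uses this reasoning itself. In section 6.4.2 it sets all enrolled children as the denominator for referred admission, because a proportion among referred children can mislead when referral itself is too low. SAP 6.1.2.3, 6.1.2.6 and 6.1.5.4 report both an all-recruited and a restricted denominator. Length of stay has only the restricted one.

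What is at stake is the reading on hospital burden. Protocol 3.1 names over-referral to stretched hospitals as a consequence to understand, and no planned trial outcome gives hospital days over all enrolled children.

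**Working it through.** **1. Design rates.** SAP 3.4 gives control rates of 1.5% (appropriate hospitalisation) and 1.1% (severe complication), each with a 30% change: 1.5% × 1.3 = 1.95% and 1.1% × 0.7 = 0.77%. No figure is given for length of stay, so I checked that these rates are the ones behind the stated sample size. I used the pooled two-proportion formula (two-sided 0.05, power 80%) and a design effect of 1 + (m − 1) × 0.001.

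- Severe complication: n = 13,351 per arm. India (m = 510): 13,351 × 1.509 = 20,147, and 20,147/510 = 39.5, so 40 clusters. Tanzania (m = 1,680): 13,351 × 2.679 = 35,767, and 35,767/1,680 = 21.3, so 22 clusters. Both match the plan.
- Appropriate hospitalisation: n = 13,141, giving 38.9 and 21.0 clusters, within those numbers.

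**2. Control admissions.** 1.5% + 1.1% = 2.6%, or 26 per 1,000. This is an upper bound by Day 7, because the 1.1% also counts deaths. Admissions after Day 7 have no design figure and are left out.

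**3. Assumed stays (not in the documents).** Usual stay 4 days. Extra referred admissions, 4.5 per 1,000, stay 2 days.

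| Scenario, per 1,000 enrolled | Admissions | Hospital days | Mean stay |
|---|---|---|---|
| Control | 26 | 26 × 4 = 104 | 4.00 |
| A. Only referred admissions rise | 26 + 4.5 = 30.5 | 104 + 4.5 × 2 = 113 (+8.7%) | 113/30.5 = 3.70 |
| B. Secondary admissions also fall 30% | 15 + 4.5 + 7.7 = 27.2 | 60 + 9 + 30.8 = 99.8 (−4.0%) | 99.8/27.2 = 3.67 |
| C. As A, but extra stays last 6 days | 30.5 | 104 + 4.5 × 6 = 131 (+26.0%) | 131/30.5 = 4.30 |

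B treats the whole 30% fall in severe complications as fewer admissions. A and B give almost the same mean stay (3.70 and 3.67), yet hospital days move in opposite directions. The planned contrast cannot tell them apart.

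**4. Range for A.** With usual stays of 4 to 6 days and extra stays of 1 to 3 days, the mean difference runs from −0.15 days (117.5/30.5 = 3.85 against 4) to −0.74 days (160.5/30.5 = 5.26 against 6). Hospital days rise by 13.0% and 2.9% respectively. In general, under A the mean falls whenever the extra stays are shorter than the usual one, while total days rise whenever the extra stays exceed zero.

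**5. Could such a difference be declared?** In Tanzania, 36,960 per arm gives 36,960 × 0.026 = 961 control admissions and 36,960 × 0.0305 = 1,127 under A. With stays of 5 and 2 days the difference is −0.44 days. For an assumed SD of 3 days, power to detect it is 92% at an ICC of 0 and 47% at an ICC of 0.05. For an SD of 4 days the figures are 71% and 29%.

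**6. Stays still running at the Day 7 call.** In a simulation with gamma-distributed stays (means 5 and 2 days), cutting every stay at a Day 7 call shrank the −0.44 to −0.32. Truncation is therefore a separate measurement gap and not the source of the problem. It is also partial: SAP 6.1.1 keeps Day 7 reports made up to 30 days after enrolment, and Day 28 reports contribute.

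**The case against.** The strongest reply is that the documents do not predict milder extra admissions. Protocol 6.4.2 says the aim is to refer more children with severe disease and uses admission as the proxy for severity, so extra stays could be as long as usual or longer. That stands. It changes the direction of the distortion (scenario C) but does not make the comparison a randomised one.

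A reader might go further and infer that the plan would report a half-day improvement while hospital burden rises by 15%. That figure comes from referred admissions alone: (15 × 4 + 4.5 × 2)/19.5 = 3.54 days against 4.0, and 69 against 60 days per 1,000. The documents do not support it as the expected result. SAP 6.1.2.4 counts all hospitalised children, so secondary hospitalisations belong in the base and bring the figures towards −0.30 days and +8.7%. Applying the plan's other design effect reverses the change in days. Neither document calls a shorter stay better.

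Over-referral is also measured elsewhere. Referral, referred admission and referral of non-severe disease are all reported over all recruited children (SAP 6.1.2.3, 6.1.2.5 and 6.1.2.7), and the economic study collects hospitalisation costs. A careful reader would see admissions rise. Those outcomes count children, however, and none of them gives days in hospital by arm.

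**Conclusion.** The point holds as one of interpretation. The planned between-arm difference in length of stay is conditional on an outcome the intervention is designed to change, and its sign need not match the change in hospital days.

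Under scenario A the gap is −0.30 days against +8.7% in hospital days. Over the assumed stays it runs from −0.15 to −0.74 days against +13.0% to +2.9%. With both design effects applied, days fall by about 4%. All of this rests on assumed stay lengths and on 2.6% control admissions. The documents fix neither the size nor the direction.

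Length of stay is listed among the other outcomes of interest, outside the testing hierarchy of SAP 4.1, so the primary conclusions do not depend on it. This is a low-cost improvement and not a threat to the trial's main result.

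**What to change.** In SAP 6.1.2.4 and 6.2.1:

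- Report length of stay among admitted children by arm as description only, labelled as conditional on admission.
- Make the between-arm comparison on hospital days by Day 28 per enrolled child, with zero for a child not admitted. Say that second stays count towards the total and how in-hospital deaths are handled.
- Use the same loss-to-follow-up assumption as the primary analysis (SAP 6.3: alive and not hospitalised), with a complete-case check, since that assumption sets lost children to zero days.
- Use cluster-robust or GEE standard errors, because about 97% of values would be zero (100% − 2.6%) and a normal-errors mixed model fits that poorly. GEE is already the fallback in SAP 6.2.3.
- Use the caregiver report in all arms, and take the Day 28 report when the child was still in hospital at the Day 7 call.
- Use facility-record duration as a sensitivity check only. Protocol 8.1.1 and 8.2.4 limit the record search to children reported hospitalised between Day 0 and Day 7, plus referred children lost to follow-up, at facilities in the study area. Mixing the two sources could itself differ by arm.

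The cost is SAP wording, one derived variable and a summary less familiar to clinicians, which is why both measures are shown. No new data collection is needed.

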6.1.2.6 Proportion of children who completed referral as reported at Day 7 follow-up

A referral will be considered completed if a child attended a hospital, whether he/she was admitted or not. Children will be counted in the numerator if they received a referral advice (as per definition above) and their caregiver reported to have sought care in a hospital and

the follow-up date is within 7 days of Day 0, considering a + 3 days window (10th day included). The denominator will be all children recruited.

Additionally, the proportion will be calculated and reported using only children who were referred as denominator.

Children for whom no Day7 data are available or withdrew prematurely from the study will be assumed not attending a hospital by Day7.

6.1.2.7 Proportion of children with non-severe disease referred to a higher level of care on Day 0

Children with non-severe disease who received a referral advice (as per definition above) at Day0 will be counted in the numerator. The denominator will be all children recruited. Non-severe disease will be defined in a separate document.

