3.1.2 Study procedures

Research assistants (RAs) will screen and recruit participants in the waiting area prior to consultation (Day 0). Following children's caregiver informed consent, the RA will record participant name, contact details, sociodemographic details and reason for attendance prior to consultation. In case of critical and emergency cases, children will be seen immediately by the HCP. The clinical consultation will be conducted according to the trial arm of the facility allocation.

After consultation, the RA will extract information from clinical records, the caregiver and/or medical records and will document them in the database. This information includes final diagnosis, oxygen saturation and results of laboratory investigations, prescribed medication, referral or follow-up advice and usage of pulse oximeter and/or CDSA.

At Day 7 and Day 28 the RA will conduct follow-up, remotely when possible.

For caregivers who can provide a phone number at the day of enrolment, Day 7 and Day 28 follow-ups will be conducted by phone. If the initial phone call fails and the phone number is valid, at least three attempts will be made on subsequent three days at different times of the day to try to reach the caregiver. If the phone number is not valid, no other call attempts will be made and alternative follow-up options will be initiated if consented for. Except during the initial phone call, follow-up can be carried out with a caregiver other than the one who gave

consent at the day of enrolment if this person is able to provide information about the child. For caregivers who cannot provide a phone number at the day of enrolment, community mechanisms will be relied on to arrange a call with the caregiver through a community focal person, e.g. a community health worker (CHW) or a community leader. To this aim, CHWs and community leaders in the targeted study areas will be asked for their consent to have their phone numbers shared with RAs in order to contact caregivers without a phone for their Day 7 and Day 28 follow-ups. Independently on whether they provided a phone number or not, caregivers will be given the alternative option to consent for in-person Day 7 follow-up that will have to be conducted as soon as possible after all remote attempts failed. In-person Day 7 follow-ups could be conducted either at the caregiver's household or another specified community location.

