3.8 Timing for Baseline and Outcome Assessments

Baseline is defined as the date of enrolment (Day 0) and time will be measured from this point.

Follow-up will occur 7 days and 28 days after Day 0. As defined in the protocol, no time window applies to Day 7 follow-up and a window of + 7 days applies to Day 28 follow-up. Refer to “Participants timeline” section of the protocol for more details.

The components (i.e. death and hospitalisation) required for the analysis of the primary outcomes will be assessed at both Day 7 and Day 28 follow-ups. For the main analysis, date of death and date of hospitalisation will be used irrespective of when these information are collected.

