6.1.6 Follow-up outcomes

6.1.6.1 Proportion of children attending scheduled follow-up at the same facility by Day 7

Attendance of scheduled follow-up at the same facility will be evaluated from:

ξ Scheduled and unscheduled visits form

A child will be counted in the numerator if:

- a follow-up visit advice is recorded at Day 0 and
- a follow-up visit for the child is found in the scheduled/unscheduled visits form and
- the follow-up visit is within 7 days of Day 0 (7th day included) and conducted at the enrollment facility

All children recruited will be in the denominator.

Additionally, the proportion will be calculated and reported using only children for whom a follow-up visit advice is recorded at Day0 as denominator.

Children for whom a scheduled follow-up visit is not found in the scheduled/unscheduled visit form will be assumed to not have attended scheduled follow-up at the same facility by Day 7.

ξ Day 7 follow-up form

A child will be counted in the numerator if:

- a follow-up visit advice is recorded at Day 0 and
- the caregiver reports visiting a government / public facility (non hospital) between child's enrollment and Day 7 follow-up visit date and
- Day 7 follow-up date is within 7 days of Day 0, considering a + 3 days window (10th day included).

All children recruited will be in the denominator.

Additionally, the proportion will be calculated and reported using only children for whom a follow-up visit advice is recorded at Day0 as denominator.

Children for whom no Day7 data are available or withdrew prematurely from the study will be assumed to not have attended scheduled follow-up at the same facility / government or public facility by Day 7.

6.1.6.2 Proportion of children presenting for unscheduled follow-up to any health facility by Day 7

Attendance of unscheduled follow-up at any health facility will be evaluated from:

ξ Scheduled and unscheduled visits form

A child will be counted in the numerator if:

- a follow-up visit advice is not recorded at Day 0 and
- a follow-up visit for the child is found in the scheduled/unscheduled visits form and
- the follow-up visit is within 7 days of Day 0 (7th day included)

All children recruited will be in the denominator.

Additionally, the proportion will be calculated and reported using only children for whom a follow-up visit advice is not recorded at Day0 as denominator.

ξ Day 7 follow-up form

A child will be counted in the numerator if:

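### Completed referral (SAP 6.1.2.6) is limited by the date of the follow-up contact, so hospital attendances reported at a Day 7 assessment held on Days 11–30 are scored as not completed

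*SAP*

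**What the plan says.** SAP 6.1.2.6 gives the substance of the outcome as: "A referral will be considered completed if a child attended a hospital, whether he/she was admitted or not". To enter the numerator a child needs referral advice at Day 0, a caregiver report of care sought in a hospital, and a follow-up date that meets the condition "the follow-up date is within 7 days of Day 0, considering a + 3 days window (10th day included". For the main proportion, "The denominator will be all children recruited"; additionally, "the proportion will be calculated and reported using only children who were referred as denominator". For absent data the rule is: "Children for whom no Day7 data are available or withdrew prematurely from the study will be assumed not attending a hospital by Day7". There is no separate rule for Day 7 data obtained after Day 10.

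Elsewhere in the plan:

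- Protocol 6.4.2 lists the secondary outcome as reported at Day 7 follow-up, with no Day 10 limit.
- On collecting the data, SAP 3.8 states that "no time window applies to Day 7 follow-up"; Protocol 8.1.1 agrees.
- SAP 6.1.1 drops a Day 7 assessment only when it is more than 30 days from Day 0, and gives recall bias as the reason.
- SAP 3.1.2 requires at least three repeat calls over the next three days when a valid number does not answer. Caregivers may also consent to "in-person Day 7 follow-up that will have to be conducted as soon as possible after all remote attempts failed".
- The Day 7-form versions of the outcomes in SAP 6.1.6 use the same condition: "Day 7 follow-up date is within 7 days of Day 0, considering a + 3 days window (10th day included".

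**The concern.** The outcome is meant to show whether referred children reached hospital. The third numerator condition instead tests when the study team reached the caregiver. A family that followed the advice at once but was hard to contact is treated like a family that did not go.

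Completion is the step between referral advice and referral-linked admission, which is a primary outcome. If completion is understated, that pathway is misdescribed: a shortfall caused by late contact would look like caregivers not following advice. Nothing planned would expose it, because the sensitivity analyses in SAP 6.2.4 cover the primary outcomes only.

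**Working it through.** The plan gives no figure for this outcome, so there is none to reproduce. The check sets the definitions side by side and then sizes the effect under stated assumptions.

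**1. Which date is limited.** The last qualifying day is 7 + 3 = Day 10. The parallel wording in SAP 6.1.6 names the Day 7 follow-up date, which confirms that the contact is meant. No attendance date appears among the conditions in 6.1.2.6.

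**2. Which contacts fall outside.** Retained Day 7 assessments run to Day 30, so those on Days 11–30 are accepted data that cannot count here. For a valid number, a first call on Day 7 followed by calls on Days 8, 9 and 10 uses up the window. In-person follow-up after those calls fail starts at the end of Day 10 at the earliest, and in practice from Day 11. For an invalid number, SAP 3.1.2 stops further calls and moves to the alternatives, so in-person contact by Day 10 is possible and would count.

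**3. One child under two rules.** Take a child referred and admitted on Day 0, with the Day 7 assessment held on Day 12.

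- Under 6.1.2.3, admission by the end of the day after Day 0 counts. SAP 3.8 uses the hospitalisation date whenever it was collected. The child is in the numerator.
- Under 6.1.2.6, Day 12 is later than Day 10. The child is out of the numerator and still in both denominators.

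The child is therefore recorded as admitted because of a referral that was not completed.

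**4. Size.** Let c be true completion among referred children and L the share of completers whose Day 7 contact fell after Day 10. Both are assumptions. Scored completion = c × (1 − L):

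| c | L = 5% | L = 10% | L = 20% | L = 30% |
|---|---|---|---|---|
| 50% | 47.5% | 45% | 40% | 35% |
| 70% | 66.5% | 63% | 56% | 49% |
| 90% | 85.5% | 81% | 72% | 63% |

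The loss is c × L, from 0.50 × 0.05 = 2.5 points to 0.90 × 0.30 = 27 points. With all recruited children as denominator, the relative loss is still L but the absolute difference is smaller.

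**5. If lateness differed by arm.** With c = 70% in both arms:

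- L = 10% in control and 20% in intervention gives 63% and 56%. The odds ratio is (0.56/0.44)/(0.63/0.37) = 0.75, with no true difference.
- With the late shares exchanged, it is 1.34.

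These show only that either sign is possible.

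**The case against.** The strongest defence is that the window is deliberate. It recurs in 6.1.2.8 and 6.1.6, the missing-data sentence of 6.1.2.6 speaks of attendance by Day 7, and a late call may report a later attendance. A limit on contact is then a rough proxy for the Day 7 horizon and also shortens recall. The purpose is reasonable. For cure status in 6.1.2.8, which is the child's state at the contact, a limit on contact date is a natural choice. Attendance is a past event, however, and here the proxy discards attendances known to be in time. Recall already has its own 30-day rule.

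A reader might also infer more than the documents support:

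- *That SAP 3.8 contradicts 6.1.2.6.* It does not. The absence of a window there concerns data collection, and a narrower scoring window can coexist with it.
- *That in-person follow-up is lost as a class.* Only contacts after Day 10 are lost, and the mix of contact routes is not given.
- *That the arms are biased against each other.* No mechanism is documented. Protocol 7.2 has the phone assessor blinded to arm and facility, although SAP 3.3 calls the study open-label.
- *That the late share is known to be large.* The nearest benchmark is the pilot target in Protocol 6.4.1 of 90% of caregivers reachable by phone on Day 7. It is a target for all caregivers, not an observed rate among completers.
- *That every visit date is already held.* The SAP names dates of death and hospitalisation. Arrival dates come from referral-facility records, searched only within the study area (Protocol 8.2.4). A date for every attendance without admission is not confirmed.
- *That children with no contact should be treated as missing.* That is a separate, explicit rule, and this argument does not reach it.

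**Conclusion.** The point holds as a misclassification in one secondary outcome. Completed referral is understated whenever any completer's Day 7 contact falls after Day 10, by the proportion L. At an assumed 70% true completion, that means a scored value between 66.5% and 49% for late shares of 5% to 30%. The mechanism follows from the SAP's wording; the size rests wholly on assumed values of c and L. The primary outcomes are unaffected, because they use event dates irrespective of when those were collected.

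**What to change.** In SAP 6.1.2.6, remove the Day 10 condition on the follow-up date. Count a referral as completed if hospital attendance is reported at any Day 7 assessment retained under 6.1.1 (to Day 30). Where an attendance or admission date is available, from the caregiver or the hospital record, use it to restrict to attendance by Day 7. Report the Day 10-limited version as a sensitivity analysis, so that the effect of the window can be seen. Review the same contact-date condition in the Day 7-form outcomes of 6.1.6.

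The cost is SAP wording and one further analysis run, with no new data collection. The downside is that, where no visit date exists, a few attendances after Day 7 may be counted, with slightly longer recall.
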